Synergy between the two anticancer agents, 5-fluorouracil (5-FU) and cisplatin is well-known in the oncological setting. Administered as a systemic treatment, cisplatin+5-FU provides improved outcomes for a range of epithelial cancers (3). In dermatology, the pyrimidine analog 5-FU is already a mainstay, approved for topical treatment of actinic keratosis and superficial BCC (4). However, efficacy is dependent on skin absorption and exposure dose; applied alone, the standard 5-FU regimen (5%, 50 mg/g) of twice daily application over 4 weeks shows limited penetration and high rates of treatment failure for deep-laying tumors (5, 6). Similarly, cisplatin is a widely used and highly potent anticancer agent with activity against BCC, but the compound's ability to penetrate intact skin is low (7, 8). At present therefore, the synergy demonstrated by cisplatin+5-FU has yet to be exploited as a topical strategy for BCC in the dermatological setting.

Ablative fractional laser (AFL) is a drug delivery modality that is steadily being implemented into dermatological practice (9). AFL induces localized tissue vaporization leaving microscopic thermal ablation zones (MAZs) surrounded by a rim of coagulated tissue in treated skin. By significantly reducing the skin's barrier function, these channels provide an effective and gentle route for topical drug delivery. Compared to systemic therapy, AFL enables the use of significantly lower drug doses, with the vast majority of the delivered dose being confined to the target skin (dose: 100 mg/m² vs 0.25 mg/cm² (cisplatin); 400-600 mg/m² vs 6.25 mg/cm² (5-FU)). As a result, side effects associated with systemic drug therapy can be avoided. Reasonable efficacy was recently reported in 28 sBCC patients after AFL-assisted delivery of topical 5-FU cream (left under 7-day

occlusion), with no adverse effects and transient local skin reactions (16). We hypothesize that therapeutic outcome can be further enhanced by combination with cisplatin.

In a recently concluded preclinical phase, we confirmed that AFL enhances penetration of cisplatin and 5-FU in *in vivo* and *in vitro* skin (10, 11). In an additional study in live pigs over 5 days, drug biodistribution and *in vivo* effects following the proposed combination treatment was assessed. In that study, using the same low dose topical AFL-assisted cisplatin+5-FU treatment, we found improved skin uptake of both drugs and enhanced, localized inflammatory reactions. Importantly, despite topical exposure over large skin areas ($>100 \text{ cm}^2$), systemic cisplatin and 5-FU uptake remained undetectable measured hourly from 0-5 hours and at 48 and 120 hours using highly sensitive mass spectrometry techniques. Overall, treatment was well-tolerated and no systemic effects were observed. Supporting a synergistic mechanism, local effects were significantly greater when cisplatin and 5-FU were applied together (11). Already well-known as a systemic therapy in the oncology setting, the dual-drug, cisplatin+5-FU strategy may hold potential as a local treatment alternative for BCC lesions.

2. Aim

In an effort to develop a new topical treatment for BCC using synergistic chemotherapeutics, this study aims to investigate tolerability, tumor size and BCC clearance following AFL-assisted cisplatin+5-FU therapy in patients with BCC.

3. Study Design

3.1 Design

A prospective clinical, uncontrolled, open-label, explorative phase IIa trial* on patients with histologically- confirmed superficial and nodular BCC

3.2 Randomization and Blinding

Due to the uncontrolled open-label study design, no randomization/blinding is planned.

*Phase IIa trial: Small preliminary clinical trials to evaluate safety and/or efficacy in selected populations of patients with the disease or condition to be treated, diagnosed, or prevented. Objectives may focus on dose-response, type of patient, frequency of dosing, or numerous other characteristics of safety and efficacy.

3.3 Intervention Summary

For a detailed description of interventions, please see Section 5.

Patients will receive AFL-assisted cisplatin+5-FU as a treatment for their BCC. In brief, treatment areas consisting of tumors and a 5 mm margin will undergo AFL exposure (Ultrapulse DeepFx CO₂ laser, Lumenis, Santa Clara, CA, USA) followed by 60 min topical application of a marketed and commercially available IV cisplatin solution (0.1% Accord Healthcare Limited A/S) at a dose of 0.25 ml per cm². After removal of cisplatin, a commercially distributed 5-FU cream (5% Efudix®, Meda Pharmaceuticals A/S) will be applied to the treatment area at a dose of 0.125 ml per cm² and left under occlusion. After skin evaluations on Day 1 and 5 after treatment, the same 5-FU dose will be applied, again left under occlusion. In total, 5-FU will remain on the skin for 7 days after AFL treatment whereafter it will be washed off.

An additional repeat AFL-cisplatin+5-FU treatment on Day 30 will be offered if tumors persist, based on clinical evaluation and imaging on Day 30.

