3.4 Summary of Outcome Measures and Methods

Outcome measures and methods/techniques are summarized below. Detailed descriptions are presented in Section 6 and Table 1 (Appendix 1).

Primary outcome:

To investigate tolerability of topical AFL-assisted cisplatin+5-FU therapy for BCC by evaluating:

- I. Severity and duration of clinical local skin reactions including erythema, edema, scabbing, flaking and pustulation assessed by a physician using an established 0-4 point scale (none, mild, moderate, severe) from 0-30 days post-treatment.

- II. Occurrence of side effects (prolonged erythema/edema, hyper/hypopigmentation, scarring and infection) up to 3 months post-treatment.

Secondary outcome:

- 1) To monitor BCC tumor size and clearance based on clinical assessments and dermoscopy, supported by non-invasive imaging techniques including dynamic optical coherence tomography (D-OCT), reflectance confocal microscopy (RCM), high intensity focused ultrasound (HIFU) and histological analysis up to 3 months post-treatment.

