3.4 Study Duration and Schedule

Patients will partake in 7 visits over a 3 month period at the dermatological department of Bispebjerg Hospital (time schedule in Section 5):

- 1 Screening visit
- 1 Treatment day
- 5 Control visits after treatment on Day 1, 5, 14, 30 and Month 3

The study is expected to run between March 2018 - March 2019

Recruitment start	1. March 2018
Treatment start	1. March 2018
Final patient treatment	1. December 2018
Final control visit	1. March 2019

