5.2.4 Topical 5-Fluorouracil (5-FU)

After cisplatin removal, the well bandage is disposed of and a thick amount of Efudix® 5% 5-FU cream (Meda Pharmaceuticals A/S, UK) is applied to the entire test area (corresponding to up to 0.125 ml per cm² skin). After 5-FU application, transparent dermatological film (TegaDerm® film dressing, 3M Medical, MN, USA) is applied to the test area as an occlusive dressing. The cream is left on the skin until next control visit. Thus, on Day 1 and 5, Efudix cream is reapplied at the same dose. The cream is removed on Day 7 after AFL treatment.

STUDY SET UP	Visit 1 Screening	Visit 2 Treatment Day 0	Visit 3 Day 1	Visit 4 Day 5 +/- 2 days	Visit 5 Day 14 +/- 3 days	Visit 6 Treatment* Day 30 +/- 5 days	Visit 7 Month 3 +/- 5 days
Screening & enrolment							
Informed consent	✓						
Inclusion/exclusion criteria	✓						
Relevant medical history	✓						
Location of BCC	✓						
Pregnancy test when relevant		✓				✓	
Interventions							
AFL		✓				(✓)	
Apply topical cisplatin(60min)		✓				(✓)	
Apply 5-FU under occlusion		✓	✓	✓		(✓)	
Clinical LSR evaluation							
FDA-approved LSR scale		✓	✓	✓	✓	✓	
Clinical photos		✓	✓	✓	✓	✓	
Safety							
Clinical evaluation		✓	✓	✓	✓	✓	
Tumor size and clearance evaluation							
Clinical/dermoscopic photos		✓	✓	✓	✓	✓	
D-OCT		✓				(✓)	
RCM		✓					
HIFU		✓				(✓)	
Biopsy							✓

*Offered if BCC residual or recurrence; (✓): Treatment/technique can be relevantly applied if tumor residuals are identified clinically or by D-OCT/RCM and there is no crusting etc. LSR: Local skin reactions, RCM: Reflectance confocal microscopy, D-OCT: Dynamic optical coherence tomography

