5.4 Compliance

All treatments are performed at the dermatological department, Bispeberg Hospital reducing the need for compliance-ensuring efforts. Securing adequate 5-FU occlusion will occur on control visits.

6. Outcome Measures & Methods

Outcome measures are evaluated in a non-blinded manner by physicians at the department of dermatology, Bispebjerg Hospital.

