6.1 Primary Outcome

Tolerability measured as:

I) Local Skin Reactions (LSRs)

Non-blinded, clinical evaluation of erythema, edema, flaking, crusting/scabbing and pustulation in treated areas will be performed by a physician using a FDA-approved 0-4 point LSR scale at Days 1, 5, 14 and 30 after AFL exposure (Appendix 1). Standardized,

clinical photographs are taken to document LSRs at each visit.

II) Side Effects

Non-blinded, clinical evaluation of prolonged erythema or edema, hyper- or hypopigmentation, scarring and infection will be evaluated up to 3 months after initial AFL treatment.

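### A repeat cycle is offered on Day 30 but no listed visit covers the rest of it, so Month-3 clearance after up to two cycles may stand beside skin-reaction data from one

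*Combined protocol and SAP*

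**What the plan says.** Section 3.3 provides for a second cycle: "An additional repeat AFL-cisplatin+5-FU treatment on Day 30 will be offered if tumors persist". The footnote to the section 5 schedule table gives the condition as "Offered if BCC residual or recurrence", and the table brackets laser, cisplatin and 5-FU at Visit 6.

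A cycle is more than one day's work. Section 3.3 continues it: "After skin evaluations on Day 1 and 5 after treatment, the same 5-FU dose will be applied, again left under occlusion". Section 5.2.4 ends it: "The cream is removed on Day 7 after AFL treatment".

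The visit list in 3.4 (Study Duration and Schedule) has one screening visit, one treatment day and "5 Control visits after treatment on Day 1, 5, 14, 30 and Month 3". Nothing is listed between Visit 6 and Month 3.

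LSR grading is timed in four places. The outcome summary in 3.4 says "from 0-30 days post-treatment", and 6.1 says "LSR scale at Days 1, 5, 14 and 30 after AFL exposure". Section 6.3.1 gives the same days but counts them from baseline, and Appendix 1 gives Days 1 to 30. Section 6.1 counts side effects for three months from the initial laser treatment. Section 6.2 sets histology at three months from the first treatment, whether or not a repeat was given. Section 9 does not mention the number of cycles.

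**The concern.** LSRs are the first component of the primary outcome, and 9.1 makes tolerability the main objective, judged against the efficacy seen. If the schedule is followed as listed, the LSR data describe one cycle while Month-3 histological clearance describes up to two. A reader could then credit two-cycle clearance with one-cycle skin tolerability.

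Section 8.2 records LSR-scale items as LSRs and not as adverse events, even when they need treatment. A marked second-cycle erythema might therefore have neither a scheduled grade nor an adverse event entry. A grade that was never taken cannot be recovered at analysis.

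Pooling also mixes follow-up times. Retreated patients reach Month 3 sooner after their last exposure, which matters for side effects defined by duration, such as prolonged erythema.

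**Working it through.** The plan gives no figure of its own to reproduce. Section 9.1 states that no formal sample size calculation was done.

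**Inputs**
- Visit 6: Day 30 ± 5, so Days 25 to 35 (section 5 table).
- Visit 7: Month 3 ± 5 days (same table). Month 3 is taken as Day 90, so Days 85 to 95. This is an assumption, but the study calendar fits it: 1 December 2018 (final treatment) to 1 March 2019 (final control visit) is 31 + 31 + 28 = 90 days.
- Offsets within a cycle: 5-FU reapplied at +1 and +5 and removed at +7; LSRs graded at +1, +5, +14 and +30.
- Planned maximum: 12 + 12 = 24 patients (9.1).

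**Step 1: does any later visit fall on a second-cycle time point?** Add the offsets to the day of the repeat.

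| Repeat on | +1 | +5 | +7 | +14 | +30 |
|---|---|---|---|---|---|
| Day 25 | 26 | 30 | 32 | 39 | 55 |
| Day 30 | 31 | 35 | 37 | 44 | 60 |
| Day 35 | 36 | 40 | 42 | 49 | 65 |

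The only visit after Visit 6 opens on Day 85, so none of the five points coincides with a listed visit. LSR gradings at listed visits are 4 of 4 in cycle 1 and 0 of 4 in cycle 2. 5-FU reapplications at listed visits are 2 of 2 and 0 of 2.

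**Step 2: time since last treatment at Month 3.**
- Two cycles: 90 − 30 = 60 days; shortest 85 − 35 = 50, longest 95 − 25 = 70.
- One cycle: 90 days, range 85 to 95.
- Section 7.2 expects local effects to resolve within 30 days. The next listed visit after a repeat comes 50 − 30 = 20 to 70 − 30 = 40 days after that point.

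**Step 3: the four LSR timings reduce to two meanings.**

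| Place | Counted from | Could cover cycle 2? |
|---|---|---|
| 3.4 outcome summary | treatment | yes |
| 6.1 | laser exposure | yes |
| 6.3.1 | baseline | no |
| Appendix 1 | Days 1 to 30 | no |

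**Step 4: possible size.** The documents give no expected number of retreated patients (k), nor of retreated patients clear at Month 3 (m). Both are assumptions, shown only as a range.
- Share of delivered cycles without scheduled LSR grading = k/(24 + k): 0/24 = 0%; 6/30 = 20%; 12/36 = 33%; 24/48 = 50%. The last needs every patient to be retreated.
- Gap between up-to-two-cycle clearance and one-cycle clearance with retreated patients counted as not cleared = m/24: 0 points at m = 0; 3/24 = 12.5 points; 6/24 = 25 points.

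**The case against.** The strongest reply is that a repeat treatment means the whole regimen. The offsets for 5-FU are counted from treatment, so they carry over to a second cycle, and 3.3 makes the skin evaluation part of each reapplication. Section 5.4 says "All treatments are performed at the dermatological department", which implies attendance. Day-7 removal has no visit of its own in cycle 1 either, so the visit list is not exhaustive. Section 6.1 ties LSRs to laser exposure and, in the next item, side effects to the initial treatment; that contrast suggests grading after every exposure. Section 8 also promises close follow-up for 30 days after treatment. All of this stands. A reader might infer that the plan gives no timing for second-cycle 5-FU, or that second-cycle LSRs will certainly go ungraded; the documents support neither. But 6.3.1 and Appendix 1 point the other way, and the schedule table provides no place to grade.

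A reader might also infer that second-cycle harm is not captured at all. It is captured in part. Side effects, adverse events and reactions outside the LSR scale, and serious events are collected throughout. Blistering and erosion are not among the five LSR items in 6.1, so 8.2 does not exclude them. The severe-event balance in 9.1 is therefore less affected than the LSR component itself.

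Day 30 does give a one-cycle clearance reading: clinical, dermoscopic, and D-OCT and ultrasound where skin reactions allow. Section 9.3 covers clearance rates and various time points, so it can be analysed. It lacks histology, and 6.2 and Appendix 1 disagree on whether confocal microscopy is done then. The clause in 9.2 on larger differences in treatment concerns deviations, and a repeat the protocol allows is not one.

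**Conclusion.** The point holds in a limited form. Visit 6 covers the start of a repeat cycle and no listed visit covers the remainder. Whether second-cycle LSRs are graded depends on which of two timings is followed. Month-3 histological clearance combines one-cycle and two-cycle patients who differ by about 30 days in time since last treatment (90 − 60), and section 9 has no rule to separate them.

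The intervals rest on Month 3 being Day 90 and on the stated visit windows. The 0-of-4 count rests on the schedule table, 6.3.1 and Appendix 1 being followed as written. The percentages in step 4 illustrate a range that includes zero and are not estimates.

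A stronger conclusion, that power or error rates suffer, is not supported: the trial is uncontrolled and exploratory, with no formal sample size. The consequence is for the completeness of the tolerability data and for how clearance is read against it.

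**What to change.** 1. Tie LSR grading in 6.3.1, Appendix 1 and the schedule table to each laser exposure, as 6.1 words it. Grade second-cycle LSRs at least at the Day +1 and Day +5 attendances that 5-FU reapplication needs, and list those attendances in the table. If this is not done, limit the LSR conclusion to cycle 1.
2. In 6.2 and section 9, label Month-3 clearance as clearance after up to two cycles. Beside it report one-cycle clearance with retreated patients counted as not cleared, described as a conservative lower bound because some might have cleared by Month 3 without retreatment. Report Day-30 clinical and imaging clearance as well.
3. Tabulate LSRs, Month-3 side effects and time since last treatment by number of cycles.

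The cost is some wording, a little more recording at attendances a repeat already requires, and one extra tabulation. It needs no additional patients or procedures. The one-cycle clearance figure can only be equal to or lower than the up-to-two-cycle figure, so the result may look less favourable.

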3.4 Summary of Outcome Measures and Methods

Outcome measures and methods/techniques are summarized below. Detailed descriptions are presented in Section 6 and Table 1 (Appendix 1).

Primary outcome:

To investigate tolerability of topical AFL-assisted cisplatin+5-FU therapy for BCC by evaluating:

- I. Severity and duration of clinical local skin reactions including erythema, edema, scabbing, flaking and pustulation assessed by a physician using an established 0-4 point scale (none, mild, moderate, severe) from 0-30 days post-treatment.

- II. Occurrence of side effects (prolonged erythema/edema, hyper/hypopigmentation, scarring and infection) up to 3 months post-treatment.

Secondary outcome:

- 1) To monitor BCC tumor size and clearance based on clinical assessments and dermoscopy, supported by non-invasive imaging techniques including dynamic optical coherence tomography (D-OCT), reflectance confocal microscopy (RCM), high intensity focused ultrasound (HIFU) and histological analysis up to 3 months post-treatment.

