6.3 Methods for Outcome Assessment

6.3.1 Clinical Evaluation and Digital Photography

Clinical evaluation of LSRs (erythema, edema, flaking, crusting/scabbing and pustulation) in treated areas will be performed by a non-blinded physician using a FDA-approved LSR scale at Days 1, 5, 14 and 30 after baseline. The scale assesses severity of individual LSR parameters on a 0-4 points scale: none, mild, moderate, severe. Tumor size (mm) and clearance (yes or no) will also be evaluated by standard clinical dermoscopy at Day 30 and Month 3 (Appendix 1). Digital photography using a Canon Camera will be performed prior to, during, after treatment, and at control visits under standardized conditions. All images are assigned an ID-number and anonymized.

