9.2 Study populations

Treated study participants are divided into the following populations:

Per-protocol (PP) population:

Includes only patients that have completed all control visits as planned. Larger deviations such as

breach of inclusion criteria, inadequate outcome assessment or larger differences in treatment, are assessed before statistical analysis is conducted.

Intention-to-treat (ITT) population:

Includes all patients that have received treatment. In the event of missing data, the population is analyzed using the “last observation carried forward” approach to minimize bias associated with loss to follow up.

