9.3 Statistics

Non-parametric or parametric statistics are used for LSR-scores, tumor size assessment and clearance rates. Descriptive data will be presented with medians and interquartile ranges (IQR) or means and standard deviations. Wilcoxon matched-pairs test will be used to test differences between test areas at various time points. P-values will be corrected for multiple comparisons when relevant and a level of $p<0.05$ considered statistically significant. Analyses are performed by SPSS version 24 (IBM Corporation, Armonk, NY, USA).

10. Quality Control, Data Protection & Storage

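### Duration of local skin reactions is a primary outcome known only to lie between visits up to 16 days apart (24 with windows), and carrying missed grades forward distorts it; report observed visits and intervals instead

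*Combined protocol and SAP*

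**What the plan says.** Section 3.4 names "Severity and duration of clinical local skin reactions", assessed "from 0-30 days post-treatment", as the first primary outcome. Section 6.1 grades five items on the "FDA-approved 0-4 point LSR scale at Days 1, 5, 14 and 30 after AFL exposure", and Section 6.3.1 repeats the same four days. The visit table in Section 5 also ticks LSR grading on Day 0 and ticks none at Month 3. It allows windows: "Visit 4 Day 5 +/- 2 days", then ±3 days for Day 14 and ±5 days for Day 30.

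Section 8.2 records start and end dates for adverse events and adverse reactions, but reactions on the LSR scale are entered as LSRs and not as adverse events. No patient diary is described.

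On analysis, Section 9.3 says only that "Non-parametric or parametric statistics are used for LSR-scores", tumour size and clearance. It does not mention duration. Section 9.2 fills missing data in the intention-to-treat population by "last observation carried forward". Section 3.3 offers repeat treatment at Day 30 if tumour persists.

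**The concern.** Duration is a named part of the primary outcome, yet the plan does not define when a reaction starts or ends, does not collect those dates, and gives no method for summarising them. The four post-treatment gradings show only that a reaction stopped somewhere between the last affected visit and the next clear one. A duration in days would depend partly on a coding rule that the plan does not state.

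The one rule it does state works against this outcome. These reactions are expected to rise and then settle, so the last grade seen is a poor guess at a later one. Carrying it forward records a grade that nobody observed. The trial is uncontrolled, so there is no comparator arm, seen on the same schedule, in which the distortion would cancel. At stake is how the tolerability profile is described, not a hypothesis test or the sample size.

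**Working it through.** The plan states no duration figure to reproduce, so the check is interval arithmetic on its own schedule.

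**Inputs (visit table in Section 5; Sections 6.1 and 9.1).** LSR gradings at Days 0, 1, 5, 14 and 30. With windows, Day 5 can fall on Days 3–7, Day 14 on Days 11–17 and Day 30 on Days 25–35. Planned numbers are 12 superficial and 12 nodular tumours in 24 patients.

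**Step 1: width of the resolution interval.** Width = next visit − last affected visit.

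| Visits | Nominal | Shortest with windows | Longest with windows |
|---|---|---|---|
| Day 1 to 5 | 5 − 1 = 4 | 3 − 1 = 2 | 7 − 1 = 6 |
| Day 5 to 14 | 14 − 5 = 9 | 11 − 7 = 4 | 17 − 3 = 14 |
| Day 14 to 30 | 30 − 14 = 16 | 25 − 17 = 8 | 35 − 11 = 24 |

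**Step 2: what the width does to a single day.** A reaction that ends on Day 16 is coded Day 14 (last affected visit), Day 30 (first clear visit) or Day 22 (midpoint).
- Coding at either end errs by up to the full width: 16 days, or 24 with windows.
- Midpoint coding errs by up to half: 16/2 = 8 days, or 24/2 = 12.
- If resolution is assumed uniform over Days 14–30, the mean absolute error is 8 days at either end and 4 days at the midpoint.

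**Step 3: uncertain onset.** For onset between visits a and b, and resolution between visits c and d, duration lies between c − b and d − a, so its width is (d − a) − (c − b).
- Onset Day 0–1, resolution Day 14–30: (30 − 0) − (14 − 1) = 30 − 13 = 17 days.
- Onset Day 5–14, resolution Day 14–30: (30 − 5) − (14 − 14) = 25 days, or up to 35 − 3 = 32 with windows.
- A reaction still present at the Day 30 visit has no upper limit from LSR grading.

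**Step 4: effect of carry-forward at a missed visit.**
- *Day 14 missed, affected at Day 5, clear at Day 30.* The data say only that resolution fell between Days 5 and 30, a width of 25 days (35 − 3 = 32 with windows). Carry-forward scores Day 14 as affected and shrinks the apparent interval to Days 14–30. That rules out Days 5–14 without evidence.
- *Day 30 missed, affected at Day 14.* The patient is counted as still affected at Day 30, whatever happened.
- *Day 5 missed.* The Day 1 grade stands in for Day 5. Section 5.2.4 reapplies 5-FU on Days 1 and 5, and Section 7.2 expects an erosive phase after the first inflammation, so a rising reaction can be missed.

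One such patient moves the proportion affected at a visit by 1/12 = 8.3 percentage points within a subtype, or 1/24 = 4.2 points overall.

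**Step 5: what honest reporting can deliver.** At nominal visits the data identify the proportion resolved by each visit. Exact 95% limits are 21% to 79% for 6 of 12, and 29% to 71% for 12 of 24. A median that falls after Day 14 can be given only as between Days 14 and 30.

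**The case against.** The strongest reply is that the plan never commits to a duration in days. Sections 6.1 and 6.3.1 and Appendix 1 turn the outcome into grades by visit, and Section 9.3 summarises those grades. A time course by visit is a fair reading of Section 3.4, and endpoint coding would be an analyst's choice. This stands in part: the coding error is possible, not planned. It does not cover carry-forward, which is planned and acts on the visit grades themselves.

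Second, prolonged erythema and oedema are followed separately to 3 months, and nothing in the plan turns on duration: the early-halt example in Section 4 concerns severity. That is correct, and it limits the importance of the point.

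Third, carry-forward acts only at missed visits, and the per-protocol population contains only patients who completed every control visit. This also stands, but that population drops the patient entirely. Using observed visits keeps the grades that were seen.

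A reader might go further and infer three things that the documents do not support:
- *That any single-number duration is wrong by up to 16 days (24 with windows).* This is the limit for endpoint coding, with actual dates, in the last interval. It is too high for midpoint coding (8, or 12) and too low when onset is also uncertain (25, or 32).
- *That most reactions resolve between Days 14 and 30.* Section 7.2 expects resolution within 30 days and does not place it after Day 14. Section 7.1 gives 5–10 days for laser redness and oedema. No distribution is given for any item under the combined treatment.
- *That an interval-censored curve solves the problem.* It reports the uncertainty without reducing it, and with 12 patients per subtype it adds little to the proportions by visit.

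**Conclusion.** The point holds as a cheap improvement. LSR duration is a primary outcome with no definition, no date capture and no analysis. Resolution is known only to within an interval of at most 16 days nominally, or 24 days with windows, when no visit is missed and the reaction is clear by the last LSR visit. The carry-forward rule assigns unobserved grades to transient reactions: it can make them look longer-lasting at later visits and milder at Day 5. The interval widths follow from the visit table alone. The effect of carry-forward depends on how many visits are missed, for which the documents give no expected figure; one patient is worth 8.3 percentage points within a subtype of 12. The exploratory design explains the absence of a power calculation. It does not remove the need to say how part of the primary outcome will be summarised.

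**What to change.** In Sections 9.2 and 9.3:

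1. Exempt LSR grades from carry-forward and analyse observed visits.
2. For each LSR item, record the last affected visit and the first later visit at which it has resolved, using actual visit dates. Define resolved as grade 0 or back to the Day 0 score.
3. Report the observed proportion still affected at each visit, by subtype, with exact confidence intervals and the number assessed.
4. Give time to resolution as an interval, right-censored at the actual Visit 6 date, or at repeat treatment if earlier. A Turnbull curve is optional.
5. Call the maximum the highest observed grade at visits, since a peak between visits is not seen.

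This needs no extra visits or patients, only analysis wording and a little programming. The cost is that duration is stated as a range instead of a single day, and the denominator is smaller wherever a visit was missed.
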